### **List of Abbreviations**

ADRD Alzheimer's Disease and related dementia

**CFR** Code of Federal Regulations

CTSC Clinical Translational Science Center

**FDA** Food and Drug Administration

**FAST** Functional Assessment Staging Tool

**GCP** Good Clinical Practice

HIPAA Health Insurance Portability and Accountability Act of 1996

**I-HoME** Improving Home hospice Management of End-of-life issues through

technology

ICF Informed Consent Form
IRB Institutional Review Board
PHI Protected Health Information

PI Principal Investigator

**REDCap** Research Electronic Data Capture

WCM Weill Cornell Medicine

# 1. Protocol Summary

**Full Title:** Adapting and implementing the Improving Home hospice Management of End-of-life issues through technology (I-HoME) intervention in caregivers of patients with Alzheimer's Disease and related dementias (ADRD).

Short Title: I-HoME and ADRD

Principal Investigator: [name], MS

**Study Description:** Aim 1 of the protocol is to adapt the I-HoME intervention for caregivers of ADRD

patients with advanced illness by leveraging stakeholder input through interviews with providers (n=30) and caregivers (n=30) of ADRD patients. Using an iterative user-centered design approach, the data collected will inform adaption of the I-HoME manual, protocol, and data collection instruments to address the care needs of patients with ADRD and their caregivers. Aim 2 of the proposal is to pilot test the adapted I-HoME intervention with family caregivers (n=30) of ADRD patients with advanced illness. Data will be collected regarding intervention feasibility and acceptability. Secondary measures will consist of ADRD symptom assessment tools, caregiver burden, caregiver anxiety and depression scores, and caregiver

satisfaction.

Sample Size: N = 90

**Enrollment:** This study will enroll 90 subjects and screen up to 300 subjects.

**Study Population:** Healthcare professionals (Aim 1 only) and adult caregivers ≥18 years old and

<105 years old who provide care to a patient with advanced ADRD (Aims 1 and

2).

**Enrollment Period:** 2 years

Study Design: Aim 1 will implement an iterative user-centered design approach through

qualitative interviews. The data collected will inform adaption of the I-HoME manual, protocol, and data collection instruments to address the care needs of patients with ADRD and their caregivers. Aim 2 will be a pilot study looking at feasibility and acceptability of implementing the I-HoME intervention for caregivers

of ADRD patients.

Description of Sites Facilities Enrolling

Participants: Participants will be recruited from Weill Cornell's Center on Aging (Aims 1 and 2)

and from the hospice medical director website (Aim 1 only).

Study Duration: 2/1/2025

**Participant Duration:** Aim 1 – 4 months

Aim 2 - 1 year

**Primary Objective:** Aim 1 - to adapt the I-HoME intervention for caregivers of ADRD patients with

advanced illness

Aim 2 - To evaluate the feasibility and acceptability of implementing the I-HoME

intervention for caregivers of ADRD patients.

Secondary Objectives: N/A Exploratory Objectives: N/A

Primary Endpoints: Feasibility outcomes are measured by examining the percentage of caregiver

participants who enroll in the study and the percentage of caregiver participants

who complete the telehealth visits.

Secondary Endpoints: Secondary endpoints will consist of ADRD symptom assessment tools (Doloplus-

2 scale and behavioral and psychosocial symptoms of dementia (BPSD) scale), caregiver burden (Zarit Burden Interview – short version), and caregiver anxiety

(General Anxiety Disorder-7 scale) and depression (Patient Health

Questionnaire-8 scale) scores.

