### 1.1.2 Hypotheses / Research Questions

We hypothesize that implementing the adapted I-HoME intervention will be feasible and acceptable to participants.

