### Recruitment

For recruitment of healthcare providers, an email will be sent out to clinicians detailing the study. A member of the research team will follow up with interested participants and schedule a time to obtain informed consent and conduct an interview (in-person, virtually).

For recruitment of caregivers, the research team will obtain a list of potential caregiver participants based on the patient's dementia diagnosis from the electronic medical record. ADRD will be defined by using a modified list of the 22 International Classification of Diseases - Tenth Revision (ICD-10) diagnosis codes endorsed by the Centers for Medicare & Medicaid Services (CMS) for ADRD.  Once a list of patients is generated, the research team will then collaborate with the patient's provider at the Center on Aging and the House Call program to identify ADRD patients with advanced illness. The research team will use the Functional Assessment Staging Tool (FAST) scale for dementia to identify qualified participants. The research team will recruit caregivers of patients who are at a stage 7a-f on the FAST scale and have not had a medical complication over the past year.

Caregivers of patients that meet the study criteria will be contacted by phone and informed about the study. Interested caregivers will be scheduled to meet (in-person, virtually) where informed consent will be obtained and an interview will be administered. Participant inclusion criteria include, (1) age 18 years or older, (2) providing care to an ADRD patient with advanced illness, and (3) English speaking.

Participants recruited in Aim 1 will be compensated with a \$75 gift certificate.

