#### Data collection

An open-ended interview guide will be developed by the research team. The objectives of the interview for the first phase of Aim 1 are (1) to identify and understand the challenges (e.g., symptom management and care needs) in caring for ADRD patients and their caregivers; (2) to describe the current I-HoME protocol and intervention to participants; (3) to understand whether the current I-HoME intervention would be feasible and acceptable to caregivers of ADRD patients; and (4) to obtain input on adapting/modifying the current intervention to meet the symptom management and care needs of ADRD patients with advanced illness.

For the second phase of Aim 1, a subset of participants from the first phase will be asked to review the adapted I-HoME materials and provide feedback on the various intervention components which include the manual, protocol, content, and data collection instruments.

#### Aim 2

Aim 2 will be a pilot study examining the feasibility and acceptability of an adapted I-HoME intervention for caregivers of ADRD patients with advanced illness.

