### Recruitment

Caregivers of ADRD patients with advanced illness will be identified from the medical records and screened by their provider. The caregiver will then be contacted by phone and informed about the study. Interested caregivers will be scheduled a time for an interview (virtually or in-person) where informed consent will be obtained. Participant inclusion criteria include, (1) age 18 years or older, (2) the family caregiver of the patient, (3) providing any sort of caregiving on a regular basis (at least weekly), (4) English speaking, and (5) have access to an electronic device with cellular data or Internet connection to access the telehealth platform.

After the caregiver is enrolled, a member of the research team will go over how to use their personal device to conduct video visits with the nurse practitioner. Software by Doxy.me will be used to conduct HIPAA compliant video visits.

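### Do Aim 2's two primary feasibility percentages need a fixed denominator, completion rule and pass mark written into the plan?

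*Combined protocol and SAP*

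**What the plan says.** Under Primary Endpoints, the Protocol Summary measures feasibility by the percentage of caregiver "participants who enroll in the study and the percentage of caregiver participants" "who complete the telehealth visits". The only screening figure is for the whole study: "This study will enroll 90 subjects and screen up to 300 subjects". Those 90 are 30 providers and 30 caregivers in Aim 1 and 30 caregivers in Aim 2. The I-HoME intervention paragraph in section 3.1 sets a ceiling of six video visits with no minimum. Table 2 times the last survey after the final visit, whichever visit that is.

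Section 1.1.2 hypothesises that "implementing the adapted I-HoME intervention will be feasible and acceptable to participants" and gives no threshold. For Aim 2, section 8 lists what will be examined: accrual, attrition, protocol adherence, device and software problems, and how often and for how long visits took place. It says the 30 caregivers are meant to establish feasibility and acceptability, not efficacy.

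On eligibility, the Protocol Summary describes caregivers aged 18 and over and "<105 years old who provide care to a patient with advanced ADRD". Section 4.2 requires age under 100, and section 4.3 excludes only those over 100. The Aim 2 Recruitment text in section 3.1 asks for a caregiver "providing any sort of caregiving on a regular basis (at least weekly"), a condition that sections 4.2 and 4.3 do not repeat.

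**The concern.** A primary endpoint should be computable from its definition, and this one is not.

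- **Enrolment.** Taken literally, the percentage of participants who enrol divides the enrolled by themselves. The 300 cannot serve as denominator, because it is a planning ceiling that pools both aims and includes providers.
- **Completion.** The plan does not say whether a caregiver who stops by agreement at visit four has completed. Nor does it say how withdrawal, patient death or hospice entry counts. Patients are at FAST 7a-f, so such events are foreseeable.
- **Criterion.** A feasibility hypothesis with no threshold cannot be refuted.

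If the rule is chosen after the data are seen, the more flattering figure can be chosen with it. The eligibility inconsistencies and the order of consent and screening seem to add doubt about who is counted at all.

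**Working it through.** **The plan's own figure.** None is given for either percentage. The only power statement (80%, section 8) concerns the Doloplus-2 pain score, a secondary outcome. The stated inputs give d = 0.40 × 8.3 / 6.5 = 0.511. Assume two-sided 5% and 6.5 as the SD of change. The normal approximation is then Φ(0.511 × √30 − 1.96) = Φ(0.84) ≈ 80%. It reproduces, but says nothing about feasibility.

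**How far the completion rule can move the result.** Assume that, of 30 caregivers, 20 attend six visits, 6 finish early by agreement and 4 patients die. Exact (Clopper-Pearson) 95% intervals:

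| Rule | Result | 95% CI |
|---|---|---|
| All six visits required | 20/30 = 67% | 47–83% |
| Same, deaths removed | 20/26 = 77% | 56–91% |
| Agreed early finish counts | 26/30 = 87% | 69–96% |
| Early finish counts, deaths removed | 26/26 = 100% | 87–100% |

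A second model assumes each of six visits is attended independently with probability 0.90:

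- All six: 0.9⁶ = 53.1%.
- At least five: 53.1% + 6 × 0.9⁵ × 0.1 = 88.6%.
- At least four: 88.6% + 15 × 0.9⁴ × 0.1² = 98.4%.

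**Enrolment.** With 30 enrolled and an assumed 60 contacted, 30/60 = 50% (37–63%). If 10 of the 60 prove ineligible and are removed, 30/50 = 60% (45–74%).

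**What a threshold would mean at n = 30.** A result of 21/30 = 70% has an interval of 51–85%. For the lower limit to exceed 60%, 70% or 80%, 24, 27 or 29 completers are needed (lower limits 61.4%, 73.5%, 82.8%).

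**What would be reported anyway.** The distribution of visits per caregiver, which section 8 promises as visit frequency, gives the all-six, at-least-five and at-least-four figures directly. Attrition separates those who left. The variants that remove deaths also need the reason for leaving. Table 1 as shown lists hospice entry but not death.

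**Consent and screening order.** Four places bear on this:

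- Section 3.1 (Aim 2 Recruitment): caregivers are found in the records and screened by the provider, then contacted, then consented.
- Section 4.4: charts are reviewed and a study physician approves eligibility before consent and screening.
- Section 7.2.3: consent is taken just before the screener.
- Table 4: patient and family-caregiver screening are Pre-Study, and consent is on Day 1.

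One sequence fits all four: record-based pre-screen, consent, then screener. Table 4 simply does not give the post-consent screener its own row.

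**Eligibility lists.**

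- The age limits differ only for caregivers aged 100 to 104.
- Weekly care is stated as an Aim 2 criterion in section 3.1 and is not contradicted by section 4.2.
- The device exclusion in section 4.3, headed for all aims, is absent from the Aim 1 inclusion list, but Aim 1 caregivers are in neither Aim 2 percentage.
- On disease stage in Aim 1, section 3.1 states that "The research team will recruit caregivers of patients who are at a stage 7a-f on the FAST scale", which agrees with the section 4.3 exclusion. The section 4.2 Aim 1 list is merely silent.

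**The case for a change.** The strongest case for a change is that these two percentages are the whole named primary endpoint and that a rule settled late can move one of them by 33 points (67% to 100% in the example). Writing definitions down would cost a short amendment and a screening log, with no extra participants. A pilot needs no hypothesis test, but this one states a hypothesis and names no result that would count against it.

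Much of the factual part stands. The denominator and the completion rule are absent from the protocol, and the arithmetic is right. Less stands of the inference. The splits are assumptions with no source in the documents. The choice of rule would not be hidden, because the visit counts and attrition are to be reported too. The rules that would replace the silence are themselves judgement calls: counting a patient's death as non-completion lowers the figure for a reason unrelated to whether the visits are feasible, while removing deaths raises it. Any threshold would have to be invented, and one set on the lower confidence limit is severe at this size (27 of 30 for 70%). Fixing a visit count now would also be premature. The six-visit ceiling belongs to the current intervention, and Aim 1 seeks feedback on components "which include the manual, protocol, content, and data collection instruments".

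The gap over death is fair. It is limited, however, because a caregiver whose patient dies would still appear in attrition, and the data-collection forms are not part of the document.

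**Conclusion.** No change to the plan is called for. The Primary Endpoints wording lacks detail, but an analyst would fill it sensibly: Aim 2 caregivers enrolled over those contacted, completers over all enrolled, with the visit distribution and reasons for stopping shown beside them. With 30 caregivers the estimates are rough under any rule (21/30 has an interval of 51–85%), and nothing in the documents ties a decision to a particular percentage. The absence of a threshold is a fair choice for a pilot of this kind.

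The nearby inconsistencies do not alter this. The age limits are a clerical slip affecting caregivers aged 100 to 104, probably few. Weekly care is covered by reading sections 3.1 and 4.2 together. The device point cannot reach Aim 2, and the consent passages are compatible.

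The conclusion rests on the measures listed in section 8 being reported in full, visit counts above all. If only the two headline percentages were published, the spread of 67% to 100% in the example would be a real ambiguity for the reader.

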# 1.1 Study Objectives

# 1.1.1 Objectives

Aim 1: To adapt the I-HoME intervention for caregivers of ADRD patients with advanced illness by leveraging stakeholder input through interviews with providers (n=30) and caregivers (n=30) of ADRD patients.

Aim 2: To pilot test the adapted I-HoME intervention with family caregivers (n=30) of ADRD patients with advanced illness.

### 1.1.2 Hypotheses / Research Questions

We hypothesize that implementing the adapted I-HoME intervention will be feasible and acceptable to participants.

### 2. Background and Significance

Use of palliative care services in the US has risen steadily over the past few decades, with over 80% of hospitals having a palliative care team¹ and over 50% of Medicare decedents receiving hospice services.² In the 1980s, most palliative care services were delivered to cancer patients.³ However, there has been a marked shift in the types of patients receiving these services today. In particular, the number of patients with Alzheimer's Disease and Related Dementias (ADRD) who need and/or receive End-of-Life (EoL) care has increased steadily. Dementia is now the fifth leading cause of death⁴ among older adults, and of all patients receiving hospice care, 45% have a primary or secondary dementia diagnosis.⁵ Yet, research focused on developing and testing services and models to best meet the palliative care needs of ADRD patients and their caregivers remains modest. As a result, multiple organizations have called for research to improve palliative care in affected patients and their caregivers. 6-8

ADRD patients with advanced illness present unique challenges for care provision when compared to patients with non-dementing terminal illnesses. One notable challenge is an inability to clearly communicate their symptoms or care needs. Patients are also more likely to exhibit behavioral and psychosocial symptoms of dementia (BPSD). These issues pose a challenge for caregivers and providers with respect to assessing and managing symptoms and providing optimal palliative care. Furthermore, caregivers of patients with (vs. without) ADRD that are approaching the EoL are more likely to suffer from depression, anxiety, and poor physical health. Therefore, supporting family caregivers of ADRD patients with advanced illness who need palliative/EoL care services is essential for their well-being and for the well-being of affected patients.

To date, little research has focused on finding solutions to improve palliative/EoL care outcomes among ADRD patients with advanced illness and their caregivers. In a recent systematic review examining ADRD patients receiving hospice care, the authors identified only 10 intervention studies, with 3 reporting ambiguous objectives or equivocal outcomes. In addition, many providers lack formal training in how to deliver palliative care to ADRD patients and evidence-based practices are lacking. Given the dearth of high quality evidenced-based solutions, ADRD patients with advanced illness and their caregivers may receive suboptimal palliative care, leading to unwanted outcomes such as burdensome care transitions, especially among African American and Latinx patients.

The Improving **Ho**me hospice **M**anagement of **E**nd-of-life issues through technology (I-HoME) intervention is a caregiver-directed intervention that supplements existing care with video visits and education provided by a palliative trained nurse practitioner. Visits with a nurse practitioner focus on assessing and treating distressing

patient symptoms and supporting caregivers through education around symptom management. However, I-HoME was not designed to account for the special care needs and challenges of ADRD patients. This protocol aims to adapt the I-HoME intervention for caregivers of ADRD patients with advanced illness.

# 3. Study Design and Methods

### 3.1 Overall Design

### Aim 1

A user-centered design approach will be incorporated and involve healthcare providers and caregivers of patients with ADRD.

For the first phase of Aim 1, the study will recruit (n=30) geriatricians and palliative care providers at Weill Cornell Medicine along with hospice medical directors from a national registry. In addition, caregivers (n=30) of ADRD patients with advanced illness will be recruited from Weill Cornell Medicine. Data collected in this phase will be used to adapt the current version of the I-HoME intervention.

For the second phase of Aim 1, as part of the iterative user-centered design process, participants from the first phase will be recruited to provide additional feedback (see Follow-up Questionnaires with submitted data collection material) on the adapted version of I-HoME to further refine the intervention.

### Study population

Healthcare providers will be recruited from Weill Cornell Medicine and a hospice medical director website (hmdcb.org). Caregivers of ADRD patients will be recruited through referrals from providers at the Center on Aging and the House Call program at Weill Cornell Medicine.

### Recruitment

For recruitment of healthcare providers, an email will be sent out to clinicians detailing the study. A member of the research team will follow up with interested participants and schedule a time to obtain informed consent and conduct an interview (in-person, virtually).

For recruitment of caregivers, the research team will obtain a list of potential caregiver participants based on the patient's dementia diagnosis from the electronic medical record. ADRD will be defined by using a modified list of the 22 International Classification of Diseases - Tenth Revision (ICD-10) diagnosis codes endorsed by the Centers for Medicare & Medicaid Services (CMS) for ADRD.  Once a list of patients is generated, the research team will then collaborate with the patient's provider at the Center on Aging and the House Call program to identify ADRD patients with advanced illness. The research team will use the Functional Assessment Staging Tool (FAST) scale for dementia to identify qualified participants. The research team will recruit caregivers of patients who are at a stage 7a-f on the FAST scale and have not had a medical complication over the past year.

Caregivers of patients that meet the study criteria will be contacted by phone and informed about the study. Interested caregivers will be scheduled to meet (in-person, virtually) where informed consent will be obtained and an interview will be administered. Participant inclusion criteria include, (1) age 18 years or older, (2) providing care to an ADRD patient with advanced illness, and (3) English speaking.

Participants recruited in Aim 1 will be compensated with a \$75 gift certificate.

#### Data collection

An open-ended interview guide will be developed by the research team. The objectives of the interview for the first phase of Aim 1 are (1) to identify and understand the challenges (e.g., symptom management and care needs) in caring for ADRD patients and their caregivers; (2) to describe the current I-HoME protocol and intervention to participants; (3) to understand whether the current I-HoME intervention would be feasible and acceptable to caregivers of ADRD patients; and (4) to obtain input on adapting/modifying the current intervention to meet the symptom management and care needs of ADRD patients with advanced illness.

For the second phase of Aim 1, a subset of participants from the first phase will be asked to review the adapted I-HoME materials and provide feedback on the various intervention components which include the manual, protocol, content, and data collection instruments.

#### Aim 2

Aim 2 will be a pilot study examining the feasibility and acceptability of an adapted I-HoME intervention for caregivers of ADRD patients with advanced illness.

### Study population

This study will recruit caregivers from the Center on Aging and the House Call program at Weill Cornell Medicine through referrals from providers.

### Recruitment

Caregivers of ADRD patients with advanced illness will be identified from the medical records and screened by their provider. The caregiver will then be contacted by phone and informed about the study. Interested caregivers will be scheduled a time for an interview (virtually or in-person) where informed consent will be obtained. Participant inclusion criteria include, (1) age 18 years or older, (2) the family caregiver of the patient, (3) providing any sort of caregiving on a regular basis (at least weekly), (4) English speaking, and (5) have access to an electronic device with cellular data or Internet connection to access the telehealth platform.

After the caregiver is enrolled, a member of the research team will go over how to use their personal device to conduct video visits with the nurse practitioner. Software by Doxy.me will be used to conduct HIPAA compliant video visits.

